4.3.2 Secondary Endpoints

Overall survival: The patient's survival status is determined at each follow-up visit. After the mandated clinic visits survival status data will come from responsible cancer centres, cancer registries and national databases and include long-term passive follow-up data such as that collected through collaboration with the National Cancer Intelligence Network and the Office of National Statistics in the U.K.

Toxicity of chemotherapy: Toxicity will be assessed using CTCAE version 4.0. Only toxicities that are at least grade 2 will be recorded on the CRF

Quality of life: This is assessed using the EORTC QLQ-C30, EORTC QLQ-CR29 v2.1 and EQ-5D scales as per the schedule indicated in section 4.1.5

Health Economics: Assess the cost-effectiveness of 24 weeks adjuvant chemotherapy in comparison to observation alone; and assess the cost-effectiveness of 24 weeks adjuvant 5-FU/Capecitabine monotherapy compared to 5-FU/Capecitabine plus Oxaliplatin. Outcomes will be reported as incremental cost per DFS and incremental cost per QALY.

Establishment of a central tissue bank for patients with SBA – further details on this tissue bank can be found in section 4.2, Translational Research.

Establishment of a central repository of clinic-pathological, epidemiological and molecular profiling data of patients being treated with SBA in this trial.

5 TREATMENTS

5.1 Treatment Arms

All drugs administered as part of the Group 1 & 2 randomisations are considered Investigational Medicinal Products (IMPs) for the purposes of this protocol (this includes folinic acid).

Version 6: 16th July 2021 Page 35 of 87

Group 1: Patients will be randomised between observation and chemotherapy. Those patients who draw the chemotherapy arm and who have consented to this can go on to be randomised into the group 2 question. This is to be encouraged as it will add significant value and improve efficiency of the trial.

Group 2: Patients will be randomised to receive therapy with a fluoropyrimidine regimen or combination therapy of fluoropyrimidine plus oxaliplatin. Investigators must specify the fluoropyrimidine regimen at the time of randomisation for each individual patient. Any accepted institutional standard IV 5-FU/Folinic Acid regimen or oral capecitabine regimen may be used. The combination regimen is specified as oxaliplatin delivered as part of a standard institutional fluoropyrimidine combination regimen. Use of other fluoropyrimidine +/- oxaliplatin regimens can be discussed with the CI or his approved representative through the Glasgow CRUK Clinical Trials Unit where eligibility of the regimen will be considered.

Treatment will continue for up to 24 weeks (or 26 weeks if this is the usual duration for an institution's approved fluoropyrimidine regimen) unless stopped early for one of the reasons outlined in section 5.10. Patients with difficulty swallowing can be switched from Capecitabine to 5-FU at any point during the trial as per investigators discretion.

Patients with DPD Deficiency

Reduced activity of DPD is one of the main causes of fluoropyrimidine-related toxicity, due to the lower capacity to degrade fluorouracil into the inactive metabolites, resulting in higher exposure of fluorouracil and cytotoxic metabolites. Most often, a DPD deficiency is the result of a deleterious single nucleotide polymorphism (SNP) in DPYD, altering the DPD enzyme activity. A DPD deficiency is classified as partial if there is remaining DPD activity (e.g. 25-50% of normal). Patients with complete DPD deficiency are excluded from this study, as will be certain patients who have compound heterozygosity.

Patients who are heterozygous carriers for any of the four variants below and who are to receive intravenous fluorouracil or oral capecitabine, should have their starting dose of fluorouracil (both loading doses and infusional doses) or capecitabine (either as monotherapy or in combination with oxaliplatin) reduced by 50%. These recommendations may be revised based on updated local/national guidance, and we recommend that all patients with partial DPD deficiency are discussed with the sponsor and Chief Investigator prior to agree their starting dose:

DPYD variant				% of Fluorouracil or Capecitabine starting dose
DPYD*2A (crs3918290)	c.1905	+	1G>A;	50%
DPYD*13 (c.16	79T>G;	rs5588	36062)	50%
c.2846A>T (rs6	57376798	3)		50%

Version 6: 16th July 2021

Page 36 of 87

c.1236G>A/HapB3 (rs56038477)	50%

For patients established on treatment, who are experiencing no or clinically tolerable toxicity with fluorouracil, the dose may be cautiously escalated in subsequent cycles by 25% dose increments. Please contact the sponsor and Chief Investigator if further discussion on this issue is required.

5.2 Specific Drug Information

5.2.1 Fluorouracil

Fluorouracil is supplied as a clear, colourless or slightly yellow solution for injection. It is available as 25mg/ml and 50 mg/ml and either may be used in the trial, depending on standard supplies available at the trial site.

Please see the Summary of Product Characteristics (SmPC) for further detail.

5.2.2 Folinic Acid

Folinic Acid is available in a variety of salt forms and any brand or salt form of folinic acid may be used. However if a site chooses to switch brands during the trial, the Sponsor must be informed and sites are requested to contact CRUK Glasgow CTU. If L-Folinic Acid is used, the doses must be adjusted accordingly.

Please see SmPC for further detail.

5.2.3 Capecitabine

Capecitabine is supplied as film-coated tablets. The 150mg tablets are light peach film-coated tablet of biconvex, oblong shape. The 500mg tablets are peach film-coated tablet of biconvex, oblong shape.

Please see SmPC for further detail.

5.2.4 Oxaliplatin

Oxaliplatin is supplied as a powder for reconstitution for injection or as a solution for injection. It is available as 5mg/ml and either presentation may be used in the trial, depending on standard supplies available at the trial site.

Please see SmPC for further detail.

5.3 Dispensing, Accountability and Administration

Chemotherapy regimens will be administered as per institutional standard care and are the choice of the Principal Investigator (PI) at that site. The choice of regimen should be notified to CRUK Glasgow CTU at the time of randomisation. The suggestions below are for guidance and differences in standard practice can be permitted, e.g., doses, infusion times, infusion volumes – these must be notified to Version 6: 16th July 2021 Page 37 of 87

the sponsor for approval at the time of initiation. The use of disposable infusion pumps and PiCC or other central lines for the delivery of the fluorouracil is permitted. The choice of regimens that will be used at the site can be discussed with the Chief Investigator (CI) or his approved representative through the Glasgow CRUK Clinical Trials Unit, at the time of initiation.

Chemotherapy doses may be recalculated every cycle during treatment if it is local practice to do so e.g. automatic updates by electronic prescribing systems. Where it is not local practice to recalculate every cycle the doses MUST be recalculated if the subject's weight changes by greater than or equal to 10% from baseline. It is not recommended that BSA is capped, but if it is local practice to cap BSA then this is acceptable as long as the sponsor is notified of this at the time of site opening.

Breaks, other than due to toxicity, are not recommended. However, if the patient needs a break for reasons other than toxicity; and the Investigator believes it to be in the patient's best interest, a break of up to 3 weeks maximum is permitted. Such 'treatment holidays' must be discussed with the CRUK Glasgow CTU for approval.

Treatment on day 1 may be administered up to 48 hours before or after the scheduled day 1 for all chemotherapy regimens for administrative reasons.

5.3.1 Examples of permitted Fluoropyrimidine Regimens

5.3.1.1 Intravenous Bolus/Infusional Fluoropyrimidine Regimens

Folinic Acid 350mg IV in 250ml Glucose 5% over 2 hours D1

5-Fluorouracil 400mg/m² IV in 100ml Sodium Chloride 0.9% over 10 minutes D1 (or as an IV bolus)

5-Fluorouracil $2400 \, \text{mg/m}^2$ IV. in $1000 \, \text{ml}$ Sodium Chloride 0.9% (or via central/PICC line) over 46 or 48 hours D1

Repeat every **TWO** weeks.

For patients with **partial DPD deficiency**:

Folinic Acid 350mg IV in 250ml Glucose 5% over 2 hours D1

5-Fluorouracil 200mg/m² IV in 100ml Sodium Chloride 0.9% over 10 minutes D1 (or as an IV bolus)

5-Fluorouracil 1200mg/m^2 IV in 1000 ml Sodium Chloride 0.9% (or via central/PICC line) over 46 or 48 hours D1

Repeat every TWO weeks.

5.3.1.2 Oral Fluoropyrimidine Regimens

Capecitabine 1250mg/m² PO twice daily for 14 days D1

Repeat every **THREE** weeks.

Version 6: 16th July 2021 Page 38 of 87

For patients with **partial DPD deficiency**:

Capecitabine 625mg/m² PO twice daily for 14 days D1 Repeat every **THREE** weeks.

5.3.2 Examples of permitted Combination Fluoropyrimidine Regimens

5.3.2.1 Intravenous Combination Fluoropyrimidine Regimens

Oxaliplatin 85mg/m² IV in Glucose 5% (volume as determined by dose) over 2 hours D1 Folinic Acid 350mg IV in 250ml Glucose 5% over 2 hours concurrently with Oxaliplatin D1. Fluorouracil 400mg/m² IV in 100ml Sodium Chloride 0.9% over 10 minutes (or as an IV bolus) D1 Fluorouracil 2400mg/m² IV in 1000ml Sodium Chloride 0.9% (or via central/PICC line) over 46 or 48 hours D1

Repeat every **TWO** weeks.

For patients with **partial DPD deficiency**:

Oxaliplatin 85mg/m² IV in Glucose 5% (volume as determined by dose) over 2 hours D1 Folinic Acid 350mg IV in 250ml Glucose 5% over 2 hours concurrently with Oxaliplatin D1. Fluorouracil 200mg/m² IV in 100ml Sodium Chloride 0.9% over 10 minutes (or as an IV bolus) D1 Fluorouracil 1200mg/m² IV in 1000ml Sodium Chloride 0.9% (or via central/PICC line) over 46 or 48 hours D1

Repeat every **TWO** weeks.

5.3.2.2 Oral Combination Fluoropyrimidine Regimens

Oxaliplatin 130mg/m^2 IV in Glucose 5% (volume as determined by dose) over 2 hours Day 1 Capecitabine 1000mg/m^2 PO twice daily for 14 days starting on day 1 Repeat every **THREE** weeks.

For patients with **partial DPD deficiency**:

Oxaliplatin 130mg/m^2 IV in Glucose 5% (volume as determined by dose) over 2 hours Day 1 Capecitabine 500mg/m^2 PO twice daily for 14 days starting on day 1 Repeat every **THREE** weeks.

5.4 Trial Drug Supplies

All trial drugs for use in the trial should be taken from usual pharmacy stock; there is no provision for funding, reimbursement or discounted stock. Shelf stock will not require IMP labelling but all IMP being dispensed to patients must be labelled at site, at the time of dispensing, in accordance with all

Version 6: 16th July 2021 Page 39 of 87

applicable regulatory requirements. See separate IMP Management Document for further detail on labelling requirements.

5.5 IMP Preparation and Administration

All trial drugs for use in the trial will be prepared and administered as per accepted institutional standard. Dose banding is permitted where it is local practice to do and this must be notified to the Sponsor at the time of initiation.

5.6 Supportive Medication

Pre-medication as prophylaxis for nausea and vomiting is recommended as per local protocols. In addition, for individual patients where local vein pain is a problem during infusion, then protocols, such as increasing infusion time, piggy-backing chemotherapy with glucose infusions etc. or use of a central venous device can be instigated.

Antidiarrhoeal therapy and skin emollients may be administered as per local protocol for managing capecitabine toxicities.

5.7 Use of Calcium and Magnesium Supplements

The use of calcium or magnesium supplements is prohibited during oxaliplatin administration when given to prevent or treat acute neuropathy as this has been shown to be ineffective. However, magnesium, calcium or phosphate supplementation either orally or intravenously for patients low in these minerals as replacement therapy is permitted.

5.8 Concomitant Therapies

Surgery

Surgery is allowed during the trial for adhesive or other obstruction, intercurrent other disease or for any other clinically appropriate reason. Continuation of adjuvant chemotherapy after a break where appropriate may be permitted following discussion with the CI or his approved representative through the Glasgow CRUK Clinical Trials Unit.

Radiotherapy

Radiotherapy is not permitted during the trial.

5.9 Prohibited Medications and Potential Drug Interactions

5.9.1 Drug Interactions

The drugs listed below may interact with some of the IMPs given as part of this trial. These drugs are not considered to be a recommended standard treatment for this patient group but there may be instances where patients receive these treatments concomitantly. If this is the case, then caution should be taken as indicated below. These medications are not considered to be Non-Investigational Medicinal Products (NIMPs) for this trial.

Version 6: 16th July 2021 Page 40 of 87

This list is not intended to be comprehensive, and local practice and guidelines and SmPCs should be followed for management of all other drugs.

Warfarin and Direct Oral Anti-Coagulants (DOACs)

It is recommended that patients DO NOT receive concomitant capecitabine and warfarin as the disturbance in warfarin metabolism during capecitabine treatment is unpredictable and difficult to manage. Wherever possible the recommendation is to treat the patient with low molecular weight heparin instead of warfarin. If the Local Investigator feels there is no alternative to giving capecitabine and warfarin concurrently then these patients MUST have their anticoagulant response (INR or prothrombin time) monitored frequently in order to adjust the anticoagulant dose accordingly. Altered coagulation parameters and/or bleeding, including death, have been reported in patients taking capecitabine concomitantly with coumarin-derived anticoagulants such as warfarin and phenprocoumon. The use of DOACs alongside chemotherapy is unproven and will be established by currently ongoing clinical trials, and so use of DOACs with chemotherapy in this trial is not recommended.

Phenytoin

Increased phenytoin plasma concentrations have been reported during concomitant use of capecitabine or 5-FU and phenytoin. Patients taking phenytoin concomitantly with capecitabine or 5-FU should be regularly monitored for increased phenytoin plasma concentrations and associated clinical symptoms.

Allopurinol

Interactions with allopurinol have been observed for 5-FU; with possible decreased efficacy of 5-FU. Concomitant use of allopurinol with capecitabine should be avoided. If viewed by the investigator as necessary, then this should be discussed with the CRUK Glasgow CTU.

Antivirals

Brivudine and sorivudine MUST NOT be prescribed with capecitabine or 5-FU as they may produce a life-threatening interaction. These drugs are not licensed for use in the UK but may be prescribed in other countries. There must be at least a 4-week waiting period between end of treatment with these drugs and start of capecitabine or 5-FU therapy. Treatment can be started 24 hours after the last dose of capecitabine.

Live Vaccines

Vaccination with a live vaccine should be avoided in patients in patients receiving 5-FU or oxaliplatin due to the potential for serious or fatal infections. Vaccination with the COVID-19 vaccine is permitted

Version 6: 16th July 2021 Page 41 of 87

as long as government guidelines are followed and a live attenuated vaccine is NOT given [Please note, although the AstraZeneca/ Oxford Covid-19 vaccine contains a live adenovirus vector, it is impossible for the vaccine to replicate or cause disease in humans and is therefore considered safe in immunosuppressed patients]. Please check with Sponsor for clarification if needed, prior to administration of any Covid-19 vaccine.

Photosensitivity

In patients treated with 5-FU, prolonged exposure to sunlight is not advisable because of the risk of photosensitivity.

Concomitant medicines known to prolong QT interval

Caution is advised when oxaliplatin treatment is co-administered with other medicinal products known to cause QT interval prolongation. In case of combination with such medicinal products, the QT interval should be closely monitored.

Concomitant medicines known to be associated with rhabdomyolysis

Rhabdomyolysis has been reported in patients treated with oxaliplatin, including fatal outcomes. In case of muscle pain and swelling, in combination with weakness, fever or darkened urine, oxaliplatin treatment should be discontinued. If rhabdomyolysis is confirmed, appropriate measures should be taken. Caution is recommended if medicinal products associated with rhabdomyolysis are administered concomitantly with oxaliplatin.

5.10 Dose Modifications

Dose delay and dose reduction of all IMPs will be carried out as per institutional standard care (and SmPC for capecitabine). These can be discussed with the CI (or his approved representative) if desired.

5.10.1 Dose Modifications for Toxicity

Expected toxicities are detailed in appendix 3. Dose modifications for diarrhoea, haematological toxicity and neurotoxicity are as described below, after some general rules and observations about managing toxicity.

If any grade 1 toxicity occurs as a result of chemotherapy, then treatment will be continued, without interruption, at full dose. For all non-haematological treatment related toxicities \geq grade 3, treatment should be withheld until recovery to \leq grade 1 then restarted commencing as day one of the next cycle, if medically appropriate. Haematological toxicities should be treated as per section 5.10.2.

If patients take more than 4 weeks to recover from chemotherapy related toxicity they will receive no further protocol mandated treatment, but will still be followed up as per the BALLAD UK protocol.

Version 6: 16th July 2021 Page 42 of 87

Wherever possible, Oxaliplatin should be dose reduced (at investigator's discretion) rather than discontinued and can be given over a longer period of time. In the situation where Oxaliplatin is discontinued due to toxicity, adjuvant treatment can continue with 5-FU or Capecitabine alone if deemed appropriate by the local investigator. In this case, the dose per m² of the single agent fluoropyrimidine can be increased to the standard single agent dose of that drug as per local practice at the discretion of the Investigator. Patients will still be considered to be on BALLAD UK protocol treatment and will be followed up as per the BALLAD UK protocol.

Crossover from Capecitabine to IV 5-FU and vice-versa is permitted if this is required to control toxicity. This crossover should be managed as per institutional standards.

For toxicities or combinations of toxicities not specifically covered in detail in this protocol, doses of chemotherapy can be reduced at the discretion of the Investigator as per local practice.

Any dose modifications must be recorded on the CRF and documented in the patient notes.

5.10.2 Dose Modification for Haematological Toxicity

The following dose modifications are provided as a guideline in the event of a haematological toxicity, however Investigators are permitted to follow their local practice for the management of haematological toxicity, with all dose modifications fully documented in the patient's medical records and CRFs.

For patients on 3 weekly chemotherapy:

Neutrophils		Platelets	Dose Modification
≥1.5 x 10 ⁹ /I	and	≥75 x10 ⁹ /l	Treat with full dose on time
<1.5 x 10 ⁹ /l	and/or	<75 x 10 ⁹ /l	Delay treatment until neutrophils and platelets are above these limits and dose reduce as below

Fluoropyrimidine Regimens

Capecitabine should be modified as per SmPC in relation to grading of toxicities.

Combination Fluoropyrimidine Regimens

Capecitabine and Oxaliplatin treatment

If > 1 delay, or 1 delay of ≥ 2 weeks occurs, reduce capecitabine and oxaliplatin doses by 25% and continue at the lower dose for subsequent cycles unless further toxicity occurs.

If further delay(s) for myelotoxicity occur despite a 25% dose reduction, further dose reductions may be made, at the discretion of the local Investigator. Capecitabine dose should be further modified as per SmPC in relation to grading of toxicities

Following first cycle of chemotherapy

Version 6: 16th July 2021 Page 43 of 87

If on the day the second, or subsequent cycle, is due neutrophils are between 1.0 and 1.5 and/or platelets are between 50 and 75, delay until recovery and then reduce doses for subsequent courses by 25%

If on the day the second, or subsequent cycle, is due neutrophils are between 0.5 and 1.0 and/or platelets are between 25 and 50, delay until recovery and then reduce doses for subsequent courses by 50%. A 25% dose reduction with G-CSF would be an acceptable alternative.

If on the day the second, or subsequent cycle, is due neutrophils are <0.5 and/or platelets <25, investigators should discontinue treatment

If delay \geq 4 weeks patient will no longer be considered to be on protocol treatment, however the patient will continue to be followed up as per protocol.

G-CSF management of neutropenia will be at the discretion of the local Investigator.

For patients on 2 weekly chemotherapy:

Neutrophils		Platelets	Dose Modification
≥1.0 x 10 ⁹ /I	and	≥75 x10 ⁹ /l	Treat with full dose on time
<1.0 x 10 ⁹ /l	and/or	<75 x 10 ⁹ /l	Delay treatment until neutrophils and platelets are above these limits and dose reduce as below

Fluoropyrimidine Regimens

5-FU dose should be modified as per standard local policy.

Combination Fluoropyrimidine Regimens

5-FU and Oxaliplatin treatment

If > 1 delay, or 1 delay of ≥ 2 weeks occurs, maintain oxaliplatin and infusional 5-FU doses, but omit bolus 5-FU and continue without bolus 5-FU for subsequent doses.

If further delay(s) for myelotoxicity occur despite omitting bolus 5-FU, reduce the oxaliplatin and infusional 5-FU doses by 25%. Further dose reductions can be made at the discretion of the local Investigator.

Following first cycle of chemotherapy

If on the day the second, or subsequent cycle, is due neutrophils <1.0 and/or platelets are between 50 and 75,, reduce doses for subsequent courses by 25% (and omit bolus 5-FU from OxMdG regimen).

If on the day the second, or subsequent cycle, is due neutrophils \leq 0.5 and/or platelets \leq 50, Investigators may at their discretion reduce doses for subsequent courses by 50% (and omit bolus 5-FU from OxMdG regimen). A 25% dose reduction with G-CSF would be an acceptable alternative.

If delay \geq 4 weeks patient will no longer be considered to be on protocol treatment, however the patient will continue to be followed up as per protocol.

G-CSF management of neutropenia will be at the discretion of the local Investigator.

Use of granulocyte colony stimulating factor (G-CSF) is permitted at the discretion of the investigator in this potentially curative situation and in keeping with ASCO or other appropriate institutional or

Version 6: 16th July 2021 Page 44 of 87

national guidelines. As with all concomitant medication, its use (including dosage, duration and indication) should be accurately documented.

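### Section 5.10.2 gives conflicting dose instructions for the same low blood count in both oxaliplatin regimens and states no order of precedence; the clearest conflict is in the 2-weekly regimen

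*Protocol*

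**What the plan says.** Section 5.10.1 sends sites to section 5.10.2 for haematological toxicity. There, each regimen has a table that makes a low count on the due day the cause of a delay: neutrophils below 1.5 or platelets below 75 (3-weekly), and neutrophils below 1.0 or platelets below 75 (2-weekly). The instruction in that row is "Delay treatment until neutrophils and platelets are above these limits and dose reduce as below". Two paragraphs then follow for each combination regimen.

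**2-weekly, 5-FU and oxaliplatin**
- Delay paragraph, triggered by more than one delay or one of at least 2 weeks: "maintain oxaliplatin and infusional 5-FU doses, but omit bolus 5-FU and continue without bolus 5-FU for subsequent doses". A 25% cut of oxaliplatin and infusional 5-FU comes only if delays recur once the bolus has gone.
- Count paragraph (under *Following first cycle of chemotherapy*), for neutrophils below 1.0 or platelets 50 to 75: "reduce doses for subsequent courses by 25% (and omit bolus 5-FU from OxMdG regimen". At neutrophils of 0.5 or less, or platelets of 50 or less, a 50% cut is left to discretion, with 25% plus G-CSF as an alternative.

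**3-weekly, capecitabine and oxaliplatin**
- Delay paragraph, same trigger: "or 1 delay of ≥ 2 weeks occurs, reduce capecitabine and oxaliplatin doses by 25" per cent. Any further reduction after that is at the investigator's discretion.
- Count paragraph, mildest band (neutrophils 1.0 to 1.5 or platelets 50 to 75): "delay until recovery and then reduce doses for subsequent courses by 25" per cent. Middle band (neutrophils 0.5 to 1.0): "platelets are between 25 and 50, delay until recovery and then reduce doses for subsequent courses by 50" per cent, or 25% with G-CSF. Lowest band (neutrophils below 0.5 or platelets below 25): discontinue.

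The section describes itself as a guideline and lets investigators follow local practice. Section 5.10 likewise refers dose changes to the institution's usual care.

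**The concern.** Because a low count is what causes a delay, every count-driven delay from cycle 2 onwards also falls under a count band. Both paragraphs then speak to the same patient on the same day, and nothing says which one governs. In the 2-weekly regimen one paragraph keeps oxaliplatin at full dose where the other cuts it. Oxaliplatin is the randomised component of the second primary question, so a site that follows the protocol's own guidance should not find two answers on how much of it to give. The text is also silent on whether a delay-based and a count-based reduction, or two successive count-based reductions, add up.

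**Working it through.** **Step 1: set the paragraphs side by side.** Percentages are the oxaliplatin dose after recovery, from cycle 2 onwards. The count paragraphs say only doses; I take this to include oxaliplatin.

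| Regimen and due-day count | Delay history | Delay paragraph | Count paragraph |
|---|---|---|---|
| 2-weekly, neutrophils 0.8 or platelets 60 | one delay ≥ 2 weeks, or a second delay | 100%, bolus omitted | 75%, bolus omitted |
| 2-weekly, same counts | delays recur after bolus omitted | 75% | 75%, bolus omitted |
| 2-weekly, same counts | first delay of 1 week | no change stated | 75%, bolus omitted |
| 3-weekly, neutrophils 1.2 or platelets 60 | one delay ≥ 2 weeks, or a second delay | 75% | 75% (agree) |
| 3-weekly, neutrophils 0.8 or platelets 40 | one delay ≥ 2 weeks, or a second delay | 75% | 50% (75% with G-CSF) |
| 3-weekly, neutrophils 0.4 | one delay ≥ 2 weeks, or a second delay | 75% | discontinue |
| 3-weekly, any count that causes a delay | first delay of 1 week | no reduction stated | 75%, 50% (75% with G-CSF) or discontinue, by band |

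The first row is an express contradiction. So are the two lower 3-weekly bands once the delay trigger is met. In the last row the delay paragraph is silent. Since the 3-weekly bands cover every count that can cause a delay, its threshold of more than one delay or at least 2 weeks has no effect from cycle 2 if the count paragraph is applied.

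**Step 2: size of the 2-weekly conflict.** Inputs are the section 5.3.2.1 example doses (oxaliplatin 85 mg/m²; 5-FU 400 bolus + 2400 infusion = 2800 mg/m² per cycle) and the 12 cycles in the schedule of assessments. Assumptions: a delay of at least 2 weeks at cycle 2, all 12 cycles given, and no other change.

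- Oxaliplatin, delay paragraph: 12 × 85 = 1020 mg/m².
- Oxaliplatin, count paragraph: 85 + 11 × (0.75 × 85) = 85 + 11 × 63.75 = 786.25 mg/m². Ratio 786.25 / 1020 = 0.771, so 23% less.
- 5-FU, delay paragraph: 2800 + 11 × 2400 = 29,200 mg/m².
- 5-FU, count paragraph: 2800 + 11 × (0.75 × 2400) = 2800 + 11 × 1800 = 22,600 mg/m². Ratio 22,600 / 29,200 = 0.774, so 23% less.

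Cycle 2 is the earliest cycle the count paragraph covers, so these are the largest differences that one 25% cut can produce.

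**Step 3: overlap of the 2-weekly bands.** Neutrophils of 0.4 meet both the line for counts below 1.0 (25%) and the line for 0.5 or less (50%). This is minor, because the lower line is discretionary.

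**The case against.** The strongest reply is that this is optional guidance. Sections 5.10 and 5.10.2 both let a site use its own practice, and section 5.3 allows doses to differ with sponsor approval, so variation between sites is permitted by design. That stands, and it limits the consequence to sites that follow the guideline. It does not remove the contradiction for those sites, which section 5.10.1 directs to this text.

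A second reply is that the paragraphs can be read together, the count paragraph filling in where the delay paragraph is silent. That works for a first short delay in the 3-weekly regimen. It does not work where both speak expressly and differ, as in the first row of the table.

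Four stronger readings are tempting, and the documents do not support them.
- *That the 3-weekly text orders full dose after a first short delay.* No sentence says so. Full dose is inferred from silence, and the table row asks for a dose reduction.
- *That at a second 3-weekly delay one paragraph gives discretion and the other a further 25%.* A second delay is itself the trigger for the 25% cut. Discretion begins only when delays recur after that cut, and the count paragraph does not say its 25% is additional.
- *That 5-FU could differ by 33%.* This compares 12 × 2800 = 33,600 with 22,600 mg/m², which keeps the bolus throughout. It describes a one-week delay that does not trigger the 2-weekly delay rule.
- *That the oxaliplatin comparison is blurred or compliance cannot be judged.* Documented local practice is already compliant, and sections 5.10.1 and 5.10.2 require dose changes on the CRF. The section governs BALLAD UK only, while the analysis is pooled; for Question 1, section 7.2 shows 10 UK patients of 77. No UK share for Question 2 is legible, and no rate of low counts is given.

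**Conclusion.** Section 5.10.2 is internally inconsistent. In the 2-weekly combination regimen the same patient is assigned 100% or 75% of the oxaliplatin dose, a difference of up to about 23% in cumulative oxaliplatin and 5-FU under the cycle 2 assumption. In the 3-weekly regimen the paragraphs differ as 25% against 50% (or 25% with G-CSF) in the middle band and 25% against discontinuation in the lowest; they agree at 25% in the mildest band once the delay trigger is met. The figures are per-patient illustrations, not trial averages. The defect matters for patients at sites that use the guideline. It changes no sample size, power or error-rate figure, and the documents do not allow its effect on the pooled comparison to be estimated. No view is taken on which instruction is clinically right.

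**What to change.** The sponsor's clinical team should reconcile the delay-based and count-based paragraphs for each combination regimen. The revised text should say which prevails when both apply, say whether successive reductions accumulate, and make the count bands mutually exclusive. The test is that any combination of count, delay length and delay number leads to one instruction. Which rule that is remains a clinical decision, and the permission to follow local practice can stay.

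The cost is rewording one section by amendment and a notice to sites. No visits, tests or analyses are added. Sites used to one reading may have to change.

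### In the advisory 3-weekly capecitabine plus oxaliplatin rules, the G-CSF alternative to a 50% dose cut also covers patients whose only low count is platelets

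*Protocol*

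**What the plan says.** Section 5.10 sets the governing rule: "Dose delay and dose reduction of all IMPs will be carried out as per institutional standard care (and SmPC for capecitabine"). Section 5.10.1 nevertheless sends haematological toxicity to 5.10.2. That section presents itself as a guideline and adds that "Investigators are permitted to follow their local practice for the management of haematological toxicity".

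In the 3-weekly capecitabine plus oxaliplatin rules, platelets of 50 to 75 on the day a later cycle is due lead to a delay and a 25% cut. In the next tier, neutrophils of 0.5 to 1.0 are joined by and/or to "platelets are between 25 and 50, delay until recovery and then reduce doses for subsequent courses by 50%. A 25% dose reduction with G-CSF", the last sentence being offered as an acceptable alternative to the 50% cut. Platelets below 25 lead to discontinuation.

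On the purpose of G-CSF, the section says "G-CSF management of neutropenia will be at the discretion of the local Investigator". It closes by stating that G-CSF use "is permitted at the discretion of the investigator in this potentially curative situation and in keeping with ASCO or other appropriate institutional" or national guidelines, with the indication documented.

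In the 2-weekly 5-FU plus oxaliplatin rules, the firm cut applies at "neutrophils <1.0 and/or platelets are between 50 and 75,, reduce doses for subsequent courses by 25" per cent. For neutrophils of 0.5 or less and/or platelets of 50 or less, "Investigators may at their discretion reduce doses for subsequent courses by 50% (and omit bolus 5-FU from OxMdG regimen). A 25% dose reduction with G-CSF" is again allowed as an alternative. The table above these rules, for counts below the treatment limits, says "Delay treatment until neutrophils and platelets are above these limits and dose reduce as below".

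**The concern.** The alternative trades a smaller dose cut for growth-factor support. The section gives a reason for that trade only when neutrophils are low. Nothing in the sentence restricts it to such patients, and the and/or trigger brings in those whose only low count is platelets. Section 5.10.2 gives no platelet rationale for G-CSF.

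A site that follows the sentence literally would give a patient recovering from platelets of 25 to 50 the same dose as one recovering from 50 to 75. The protocol otherwise separates these two patients by a factor of two in the size of the cut. At stake is the oxaliplatin dose after recovery in a small group of combination-arm patients, not the trial's inference.

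**Working it through.** The plan states no figure to reproduce, so the check reads the rules band by band and works out the resulting dose.

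**Inputs**
- Oxaliplatin example dose, 3-weekly: 130 mg/m² (section 5.3.2.2).
- Oxaliplatin example dose, 2-weekly: 85 mg/m² (section 5.3.2.1).
- Cuts of 25% and 50% (section 5.10.2).
- Patient: normal neutrophils, one low platelet count (×10⁹/l) on the day a cycle is due, no earlier reduction.
- Capecitabine is left out, because section 5.10 refers it to the SmPC.

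**Formula:** dose after recovery = starting dose × (1 − cut).

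**3-weekly schedule**

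| Isolated platelets | Rule applied | Oxaliplatin, mg/m² | Relative to platelets 60 |
|---|---|---|---|
| 60 | 25% cut | 130 × 0.75 = 97.5 | 1.00 |
| 40 | 50% cut | 130 × 0.50 = 65 | 65/97.5 = 0.67 |
| 40 | 25% cut with G-CSF | 130 × 0.75 = 97.5 | 97.5/97.5 = 1.00 |

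For platelets of 40, the alternative gives 97.5 − 65 = 32.5 mg/m² more than the stated cut, or 97.5/65 = 1.50 times as much. The difference between the two platelet tiers disappears.

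**2-weekly schedule, for comparison**
- Platelets 60: 85 × 0.75 = 63.75 mg/m².
- Platelets 40: 85 × 0.50 = 42.5 mg/m² with the discretionary cut, or 85 × 0.75 = 63.75 mg/m² with G-CSF.
- If the 25% cut were made firm for all platelets below 75, with 50% kept as a discretionary deepening, platelets of 40 would still give 42.5 to 63.75 mg/m².

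The range is the same before and after such an edit, and the dose after platelets of 40 never exceeds the dose after platelets of 60. What differs is only the obligation. The neutrophil trigger has no lower bound, so the firm 25% cut carries down to 0.5 and less. The platelet trigger stops at 50, so below that only a discretionary instruction applies.

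**The case against.** The strongest reply is that the section already contains the limit. It speaks of G-CSF for neutropenia, asks that its use follow ASCO or other guidelines, and requires the indication to be recorded. An investigator would have to read one sentence alone and prescribe G-CSF to a patient with normal neutrophils. The rules are also only a guideline: institutional standard care governs oxaliplatin just as the SmPC governs capecitabine, so 65 against 97.5 mg/m² describes a non-binding text on its least favourable reading. Later delays bring further discretionary reductions, and the document does not say how often isolated low platelets occur.

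All of this stands as a limit on the consequence. It does not make the sentence right. Section 5.10.1 directs sites to 5.10.2, and advice they are told to consult should not depend on another paragraph to correct its trigger.

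The objection succeeds fully on the 2-weekly schedule. A reader might infer that platelets of 50 or less there permit a full-dose restart, or a higher dose than platelets of 50 to 75. The documents do not support either inference: the table calls for a delay and a reduction, the only reductions listed are 50%, or 25% with G-CSF, and the dose range is unchanged by tightening the wording.

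**Conclusion.** The point holds as a low-severity drafting error in one advisory sentence of the 3-weekly rules. Its size is 97.5 instead of 65 mg/m² of oxaliplatin after platelets have recovered to at least 75, in BALLAD UK patients on capecitabine plus oxaliplatin with isolated platelets of 25 to 50. This assumes the protocol's example dose, a first reduction, and a site that applies the sentence as worded instead of its own standard. The number of such patients cannot be estimated from the document.

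In the 2-weekly rules there is only a mismatch of firmness between two platelet bands, largely covered by the table, and no dose effect is claimed. Nor should a reader infer any threat to the primary result: nothing here touches the DFS analysis, power or alpha. It merits correction because it is patient-safety text and the remedy is a few words.

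**What to change.** 1. **3-weekly rules.** Restrict the alternative, for example: *Where neutrophils are 0.5–1.0 and platelets are above 50, a 25% cut supported by G-CSF may be used instead.* Isolated platelets of 25 to 50 then keep the 50% cut.
2. **2-weekly rules (consistency only).** Write the trigger for the firm 25% cut as *neutrophils <1.0 and/or platelets <75*, and leave the 50% cut for the lower band as a discretionary deepening.

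Keep the guideline status, the local-practice clause and the institutional-standard rule of section 5.10. The cost is a few words. They can be carried in the next amendment, with no extra data, visits or patients.
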